**Schema:**

Consecutive patients presenting to Grady Memorial Hospital with mandibular fractures will be evaluated for recruitment in this pilot study. Patients requiring either open reduction and internal fixation (ORIF) or closed reduction (CR) will be included in the study.

The choice of surgical method (ORIF versus CR) will be determined by the patient preference in conjunction with the attending surgeons expert opinion. The surgical procedure for closed treatment is a simple and standardized procedure involving placement of arch bars and maxillomandibular fixation (MMF) for a period of 4-6 weeks. The surgical procedure for ORIF will involve the placement of arch bars intraoperatively, exposure of fractures by intraoral or transcutaneous incisions, intraoperative MMF and ORIF. All procedures will be done under a general anesthesia. All eligible subjects will be initially stratified to ORIF or CR. Subjects within each group will then be randomized to either Stryker Hybrid arch bars or Erich arch bars (control). In all groups the arch bars will be left in place for six weeks. Stryker Hybrid arch bars will be placed according to the manufacturers instruction using a minimum of four locking screws per arch. Erich arch bars will be placed using a combination of 24 and 25 gauge wire as is the historical technique. Arch bar removal is a simple procedure that will be completed under local anesthesia in the outpatient clinic.

The primary predictor variable is the type of archbar (Stryker Hybrid versus Erich). The primary outcome variable is time required to place the arch bars. Secondary outcomes include union (nonunion, fibrous union, malunion), complications, hospital charges and need for additional procedures

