## Objectives

- 1) Is there a difference in the application time when comparing Stryker hybrid arch bars to Erich arch bars for the ORIF or CR of mandibular fractures?
- 2) Is there any difference in overall surgical time, postoperative length of stay, hospital charges, fracture healing or complications when comparing Stryker hybrid arch bars to Erich arch bars for the ORIF or CR of mandibular fractures?

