### Patient Assessment

Patients will be assessed during surgery and in the postoperative period while in the hospital. After discharge, patients will be followed routinely to ensure complete bony consolidation of the fracture and at 4 to 12 weeks postoperatively. The primary

outcome variable is application time for placement of arch bars. Secondary outcomes include intra-operative surgical time length of stay after surgical procedure, length of stay, hospital charges, fracture healing and complications.

All data will be collected by the PI or CI during the initial admission for surgery to repair the fracture or at the one week and 6 week follow-up appointments. All data will be recorded on a standard data collection sheet. Subjects will have not have any questionnaires or surveys to complete. Demographic, preoperative, operative and postoperative variables will be recorded and analyzed. Demographic data includes age, sex and race. Preoperative variables include medical history (DM and HIV), social history, fracture location, number of fractures, time from injury to surgery and antibiotic use. Operative variables include time for arch bar application, surgical time and surgical approach. Post operative variables include fracture healing, follow-up, complications and hospital charges. It is anticipated that the study will conclude at 24 months. All subjects will be paid \$50 at the 4 to 12 week follow-up visit.

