Statistical Analysis

NCT02283528

Unique Protocol ID:
IRB00076048

A Comparison of Stryker Hybrid Arch Bars Versus Erich Arch Bars for Maxillomandibular Fixation of Mandibular Fractures: A Prospective Randomized Study

Principal Investigator
[name] [name], MDSc, FRACDS, FRACDS

November 23, 2018

A data collection sheet was used to record demographic, preoperative, operative and postoperative variables. Preoperative and operative variables were compared between the treatment groups using t-tests for age, and a combination of χ^2 and Fisher's exact tests for other variables. Arch-bar application times were compared among the preoperative and operative variables using Pearson correlation for age and a combination of t-tests and one-way ANOVA. Treatment groups versus time of arch-bar application and length of surgery were tested using t-tests. Multiple regression was used after covariates were determined using stepwise linear regression. All analysis was performed using the patients' original treatment assignment (intent-to-treat). All results were considered statistically significant if the p-values were less than 0.05.

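### Four of the five Objective 2 outcomes have no between-arm analysis in the SAP, and its only criterion, p<0.05, cannot answer the healing and complication questions at 35 to 50 patients per arm

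*SAP*

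**What the plan says.** The Protocol's second objective is a yes/no question on five outcomes: "Is there any difference in overall surgical time, postoperative length of stay, hospital charges, fracture healing or complications". The Schema's list of secondary outcomes includes "complications, hospital charges and need for additional procedures", so additional procedures make a sixth.

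The SAP is one paragraph. Its only between-arm outcome comparison reads "Treatment groups versus time of arch-bar application and length of surgery were tested using t-tests". Its other between-arm comparison is of a different kind: "Preoperative and operative variables were compared between the treatment groups using t-tests for age", with χ² and Fisher tests for the remaining variables of that type. The regression sentence names no outcome. The decision rule for everything is "All results were considered statistically significant if the p-values were less than 0.05".

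Under Patient Assessment the Protocol sorts its variables by period: "Post operative variables include fracture healing, follow-up, complications and hospital charges". The same section states an intention to analyse them, "Demographic, preoperative, operative and postoperative variables will be recorded and analyzed", but gives no method.

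**The concern.** A surgeon choosing between a bar that may be quicker to place and the established one needs to know whether speed costs anything in healing or complications. Objective 2 puts that question, and the SAP sets out no analysis of it. An analyst who follows the SAP to the letter reports length of surgery and stops. One who goes further has to choose the method, the outcome definition and the handling of the ORIF/CR strata after the data are in, with p<0.05 as the only guide.

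That guide is weak for uncommon events in a small trial. A p-value above 0.05 is then compatible both with no difference and with a large one. Only an estimate with its interval shows which differences the data can exclude.

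**Working it through.** **1. Which outcomes have a between-arm analysis?**

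| Outcome | Where the Protocol asks for it | Between-arm method in the SAP |
|---|---|---|
| Surgical time | Objectives | t-test |
| Stay after surgery | Objectives | none |
| Charges | Objectives | none |
| Healing | Objectives | none |
| Complications | Objectives | none |
| Additional procedures | Schema | none |

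The χ²/Fisher sentence does not fill the gaps. It covers preoperative and operative variables, and Patient Assessment classes healing, complications and charges as postoperative. So 1 of 5 Objective 2 outcomes is covered and 4 are not.

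**2. Patients per arm.** Therapy gives 30 ORIF and 20 CR patients per arch-bar arm. The total is 2×30 + 2×20 = 100, which matches Sample size (60 + 40). Per arm this is 30 + 20 = 50. With the 30% loss allowed under Sample size, 50 × 0.70 = 35 (21 ORIF + 14 CR). Reading 100 as the number after loss would mean enrolling 100/0.70 = 143. That conflicts with the numbers randomized under Therapy and with a Budget for 100 subjects. The range used below is 35 (full loss) to 50 (none).

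**3. Power of Fisher's test.** The documents give no event rates, so the rates here are assumptions. Sidedness is not stated; two-sided 0.05 is assumed. Power = Σᵢ Σⱼ Bin(i; n, p₁) · Bin(j; n, p₂) · 1[Fisher p(i, j) < 0.05].

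| Assumed rates | 35 per arm | 50 per arm |
|---|---|---|
| 5% v 10% | 3% | 6% |
| 5% v 15% | 14% | 24% |
| 10% v 20% | 13% | 19% |
| 10% v 30% | 46% | 64% |
| 20% v 40% | 36% | 52% |

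**4. What an interval would show.** Newcombe's 95% interval for p₁ − p₂ combines the Wilson limits (l, u) of each arm. Its lower limit is d − √[(p₁−l₁)² + (u₂−p₂)²] and its upper limit is d + √[(u₁−p₁)² + (p₂−l₂)²].

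- 4/35 v 4/35: p = 0.114, Wilson limits 0.045 and 0.260. Half-width √(0.069² + 0.145²) = 0.161, so -16 to +16 points.
- 0/35 v 0/35: ±9.9 points. 7/35 v 7/35: ±18.8 points.
- 5/50 v 5/50, with no loss: ±12.7 points.
- 9/35 v 4/35 (26% v 11%): difference +14.3 points, interval -4.3 to +32.0, Fisher p = 0.22.

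The last case is non-significant, yet the interval reaches an excess of 32 points.

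**5. The one secondary test that is named.** The Schema stratifies by ORIF/CR before randomization, but the t-test for length of surgery ignores the strata. Suppose within-stratum SD is 1, the strata split 60:40 in each arm, and mean surgical time differs between strata by g SDs. The t-test then uses variance 1 + 0.6×0.4×g². The arm difference varies only with the within-stratum variance of 1, because the strata are balanced. The actual two-sided type I error is about 2·[1 − Φ(1.96·√(1 + 0.24g²))].

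- g = 1: 1.96 × √1.24 = 2.18, type I error 2.9%.
- g = 2: 1.96 × √1.96 = 2.74, type I error 0.6%.

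The test is conservative, so precision is lost that a stratum term would recover. The size of g is an assumption.

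**The case against.** The strongest reply is that the SAP's significance sentence only defines when a result is called significant. It does not say what p≥0.05 means, and neither document claims equivalence or safety. That is right. A reader might infer that a null healing or complication result will be reported as no difference, but this is a forecast of how the authors will write, and no passage states it. The gap that can be shown is the missing analysis.

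It can also be said that the Protocol does commit to analysing the postoperative variables. This stands: the intention is there, and the method is what is absent.

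The figure of 35 per arm assumes the full allowed loss. Surgical time and index-admission stay arise before follow-up and need not be affected. This is fair, and it is why the range to 50 is shown. Power for 10% v 20% is still only 19% at 50.

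Two further readings are tempting and should not be drawn. One is a high chance of a false positive across many secondary tests. The SAP names a single secondary test, the outcomes are related to one another, and Fisher's test runs below its nominal level with rare events. The other is that stay and additional procedures go uncollected because Patient Assessment leaves them out of its variable lists. Those lists need not be exhaustive, stay is named there as a secondary outcome, and the separately attached data collection sheet was not available to check.

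**Conclusion.** The concern holds in limited form. As written, the SAP leaves four of the five Objective 2 outcomes, and additional procedures, without a between-arm analysis. It judges all results by p<0.05 and asks for no estimate or interval. At 35 to 50 per arm that criterion cannot settle the healing and complication questions. Power is 13% to 19% for 10% v 20%, and equal counts leave intervals of roughly ±10 to ±19 points at 35 per arm.

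The mapping of outcomes to methods rests on the text alone. The power and interval figures rest on assumed event rates and a two-sided test. The range of 35 to 50 spans full to no loss and pools the two strata. The documents do not show that a null result will be presented as no difference; the plan simply gives no safeguard against it. The primary outcome is not affected by the missing secondary analyses.

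**What to change.** In the SAP, report every secondary outcome as a between-arm estimate with a 95% confidence interval, and state that p≥0.05 in this pilot is not evidence of no difference. Name the methods:

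- **Complications, additional procedures and healing:** analyse per patient, as a risk difference stratified by ORIF/CR (for example Mantel-Haenszel). Define healing failure as any of the three union problems listed in the Schema (nonunion, fibrous union, malunion).
- **Length of stay and charges:** a stratum-adjusted difference in means with a bootstrap interval.
- **Length of surgery:** a linear model with arm and ORIF/CR stratum in place of the unadjusted t-test.

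Confirm on the data collection sheet that stay and additional procedures are captured. The SAP is dated November 2018 and written in the past tense, so the data may already have been analysed. Label any analysis added after data collection as such.

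No new patients are needed. The cost is a little more analysis, and giving up any claim of no difference on a secondary outcome that rests on a non-significant p-value.
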